### **9.5. Definition and Reporting of (Serious) Adverse Events**

#### **9.5.1. Definition of Adverse Event and Serious Adverse Event**

An AE is any untoward medical occurrence in a patient or clinical investigation subject to whom a medicinal product is administered. The occurrence does not have necessarily a causal relationship with the treatment. An AE can therefore be any unfavorable and unintended sign (including an abnormal laboratory finding, for example), any symptom or disease, whether new or exacerbated, temporally associated with the use of a medicinal product, whether or not related to the investigational drug product.

An AE, whether or not considered to be causally related to the investigational drug product, may be:

- The deterioration of a pre-existing chronic disease or aggravation of a symptom or disease that was present at inclusion of the patient in the study.
- A symptom or disease discovered after the start of the study even if it was probably present prior to the patient's inclusion.
- Abnormal laboratory findings when they are considered as clinically significant by the Investigator.

In case a vital sign shows a clinically significant abnormality, an AE should be reported (or the abnormal vital sign should be linked to an already reported AE). A serious AE is an AE that, at any time, fulfils one or more of the following criteria:

- results in death,
- is life threatening (the patient was at risk of death at the time of the event; it does NOT refer to an event which hypothetically might have caused death if it were more severe),
- requires in-patient hospitalisation or prolongation of existing hospitalisation - hospitalisation required by the study will not be considered as an AE,
- results in persistent or significant disability/incapacity (substantial disruption of a person's ability to carry out normal life functions),
- is a congenital anomaly/birth defect,

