### **9.5.3. Adverse Event Recording and Reporting**

#### **Period of (Serious) Adverse Event Data Collection:**

In order to ensure complete safety data collection, recording and reporting, all (S)AEs occurring during the study, i.e. after signature of the Informed Consent, must be recorded, even if no study drug was administered. These include all AEs occurring, recurring, or worsening after the signature

of the informed consent. The period of observation for the study is from the screening visit to the visit.

An AE occurring between signature of PRISM 2 Informed consent and first study drug administration will be considered as TEAE of PRISM - I10E-1302.

If the Investigator becomes aware, after that period, of any unusual safety information or any safety information that appears to be drug related involving a patient who had participated in the study, even after the patient completes the study, he/she should contact the sponsor to determine how it should be documented and reported.

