#### 4.7.2 Adverse Events

All AEs occurring during the study will be classified by preferred term (PT) and system organ class (SOC) using the version 17.1 of the Medical Dictionary for Regulatory Activities (MedDRA).

- Seriousness *Serious* if one of the follow-ups is serious / *Non-serious* otherwise

- Seriousness criterion For each of the criteria listed below: *Yes* if at least one of the follow-ups had *Yes* for the corresponding criterion / *No* otherwise
  - *Results in death*
  - *Life-threatening*
  - *In patient hospitalisation or prolongation of existing hospitalisation*
  - *Persistent or significant disability / incapacity*
  - *Congenital anomaly / birth defect*
  - *Important medical event*
- Start date time Start date time of the first follow-up
- End date time End date time of the last follow-up
- Ongoing *Yes* if last sequence follow-up is ongoing / *No* otherwise
- Did the AE start within 72h after an infusion? *Yes* if the first follow-up started within the first 72h after an infusion / *No* otherwise
- Intensity maximum(Intensity of follow-ups)  
Increasing order of importance: *Mild / Moderate / Severe*
- Action taken maximum(Action taken of follow-ups)  
Increasing order of importance: *None / Dose changed / Interruption of IMP / Discontinuation of IMP*
- Corrective medication *Yes* if at least one of the follow-ups had a corrective medication / *No* otherwise
- Relationship to study drug *Yes* if at least one of the follow-ups had a relationship to study drug assessed as *Yes* / *No* otherwise
- Outcome maximum(Outcome of corresponding follow-ups)  
Increasing order of importance: *Unknown / Recovered without sequela / Recovered with sequelae / Recovering / Not recovered / Fatal*

AEs will be classified as I10E-1302 AEs or treatment emergent AEs (TEAEs) according to the date of onset:

- I10E-1302 AEs are defined as events with a date-time of onset before the start date-time of the first infusion in I10E-1306.
- TEAEs are defined as events with a date-time of onset on or after the start date-time of the first infusion in I10E-1306.

Treatment Emergent Adverse Events (TEAE)

The following rules for the derivation of the TEAE status will be used in the order of display.

1. If the date-time of the AE onset is known: TEAE = “Yes” if AE onset date-time  $\geq$  start date-time of first IMP infusion / “No” otherwise.
2. If the date-time of the AE onset is not known but the complete date of the AE onset is known:

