Duration of TEAEs will be calculated as AE end date – AE start date + 1 and presented with descriptive statistics on recovered AEs (i.e. AEs with an outcome of "Recovered without sequelae" or "Recovered with sequelae"). Statistical unit of analysis will be the individual recovered TEAE. No imputation will be performed for the purposes of computing duration.

The time between the last administration of IMP to the onset of the TEAE will be calculated as AE start date – Date of previous IMP infusion and will be presented with descriptive statistics using the individual TEAE as statistical unit.

All SAEs, drug related AEs, AEs leading to dose changes or discontinuation of IMP, and other significant AEs will be listed.

Time of onset since last administration for most common TEAEs (those which occurred in at least 10% of the patients) will be presented by patient status (naïve/pre-treated) and by course number. Summary statistics including 95% confidence intervals will be calculated for each TEAE preferred term.

I10E-1302 AEs will be listed by patient.

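### The TEAE definition has no rule for adverse events that start before the first I10E-1306 infusion and worsen after it

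*SAP*

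**What the plan says.** SAP 4.7.2 first reduces all follow-up records of an adverse event to one record. Its start is the "Start date time of the first follow-up". Intensity, seriousness, action taken and relationship to study drug each take the worst value found in any follow-up.

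The reduced event is then placed in one of two classes by onset. On one side, "TEAEs are defined as events with a date-time of onset on or after the start date-time of the first infusion in I10E-1306". On the other, "I10E-1302 AEs are defined as events with a date-time of onset before the start date-time of the first infusion in I10E-1306". Five ordered rules deal with incomplete onset dates. None of them mentions a change in intensity or seriousness. For the second class the SAP says that "I10E-1302 AEs will be listed by patient". SAP 4.3 also counts adverse events of I10E-1302 as medical history for this study.

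Protocol 12.10.1 likewise defines TEAEs by occurrence after the first dose, and sends all other events to listings. The protocol's recording sections are wider. Section 9.5.1 accepts as an adverse event the "aggravation of a symptom or disease that was present at inclusion of the patient in the study". Of the events to be recorded, section 9.5.3 says: "These include all AEs occurring, recurring, or worsening after the signature" of consent.

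**The concern.** Every patient comes straight from I10E-1302, where the same product was given at 2 g/kg and then 1 g/kg every 3 weeks. The first 0.5 g/kg dose is due on the day of that study's final visit or within 72 hours of it. An event may therefore still be open when I10E-1306 treatment starts.

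Suppose such an event was mild and becomes severe or serious after a later I10E-1306 infusion. If the site adds a follow-up to the existing record, the event keeps its old start date and takes on the new, worse attributes. It is then classed as an I10E-1302 event. If the site opens a new record instead, the same clinical course is a TEAE.

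Safety is the study's secondary objective. A count that depends on this recording habit is not well defined, and when it errs through this route it errs downwards.

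**Working it through.** The plan states no figure on this point, so the check is to trace illustrative records through TEAE rules 1 to 5 of SAP 4.7.2. The first I10E-1306 infusion is assumed to be on 10 March 2016 at 10:00. This date is for illustration only.

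| Record | Onset information | Rule | TEAE |
|---|---|---|---|
| A. Earlier event, worsening kept as follow-up | 20 Feb 2016, 08:00 | 1 | No |
| B. Same worsening entered as a new event | 2 Apr 2016, 08:00 | 1 | Yes |
| C. Earlier event, date without time | 20 Feb 2016 | 2 | No |
| D. Earlier event, partial date, investigator timing over 72 h | Feb 2016 | 3 | Yes |
| E. Partial date in the month of first infusion, timing missing | Mar 2016 | 4 | Yes |
| F. Partial date in an earlier month, timing missing | Feb 2016 | 4 | No |
| G. No onset date | none | 5 | Yes |

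The worsening is lost in A, C and F, where the recorded onset can be placed before the first infusion. It is not lost in B, D, E or G. A and B describe the same clinical course and differ only in how it was entered.

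Outputs affected in A, C and F: the SAP 4.7.2 summary of TEAEs overall and by seriousness, relationship, severity and action taken, and the TEAE tables by SOC and PT.

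Outputs not affected, or not clearly affected:
- SAP 4.7.2 lists all SAEs, drug-related events and events leading to dose change or discontinuation, without restriction to TEAEs. It also lists the I10E-1302 events.
- SAP 4.7.3 summarises laboratory values, abnormalities and shifts by visit, whatever the TEAE status. A worsening haemoglobin, for example, would still show there.
- SAP 4.1 tabulates withdrawals due to adverse events irrespective of onset. A carried-over event that led to withdrawal could be counted there and be missing from TEAEs by action taken.
- The SOC/PT sentence in SAP 4.7.2 names SAEs and drug-related events without limiting them to TEAEs, but says the counts shown are of TEAEs. Its scope is unclear.

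Size per affected patient, with N patients in the denominator: shift = 100 × 1/N percentage points. Protocol 12.3 expects 15 to 30 patients.
- N = 30: 100 × 1/30 = 3.3 points.
- N = 15: 100 × 1/15 = 6.7 points.

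This applies to a patient with no other event in the category concerned. SAP 4.10 reports early termination and the documents do not give the final number treated. The shift then is 1/N with the actual N.

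**The case against.** The strongest reply is that the documents, read together, support a new record. The I10E-1302 event is medical history (SAP 4.3), aggravation of a condition present at inclusion is an adverse event (protocol 9.5.1), and worsening after consent must be recorded (protocol 9.5.3). The aggravation would then carry an I10E-1306 onset and count as a TEAE. This reading is reasonable, but neither document states it. Taking the maximum intensity over follow-ups presupposes that severity can change within one event. Protocol 9.5.1 describes an event that becomes serious later, and protocol 11.1.2.5 foresees changes to existing events. The requirement in protocol 9.5.3 for one entry per event does not say which applies.

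A second reply concerns data flow. SAP 3 describes two databases, and SAP 4.7.2 does not say that follow-up chains from I10E-1302 are brought into the I10E-1306 data. This stands, and the remedy has to work without such a link.

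Third, the SAP follows the protocol's own analysis definition in 12.10.1, while 9.5.1 and 9.5.3 govern recording. This also stands. The gap is shared by both documents.

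A reader might infer that a carried-over event which worsens disappears from all I10E-1306 safety output. The documents do not support that. The listings, laboratory summaries and withdrawal counts remain, some incomplete dates default to TEAE, and a newly opened record is counted.

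**Conclusion.** The point holds as a gap in the TEAE definition. A worsening under I10E-1306 is excluded from the TEAE summaries when two conditions are met: it is recorded as a follow-up of the earlier event, and that event's onset can be dated before the first I10E-1306 infusion. Whether it is counted otherwise depends on the site opening a new record.

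The number of affected events is unknown and may be zero. The 3.3 to 6.7 percentage points are the effect of one affected patient at the planned 30 to 15 patients, not an estimate of bias. A reader might infer from the run-on design that events open at entry are usual. No figure in the documents supports this. The study is descriptive, so no test result is at stake. With so few patients, however, one severe or serious event missing from a table could turn a true 3.3% or 6.7% into a reported 0%.

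**What to change.** In SAP 4.7.2 and protocol 12.10.1, add a second route to TEAE status: an event with earlier onset that has a record dated at or after the start of the first I10E-1306 infusion showing higher intensity or new seriousness. Date that TEAE at the first such record, derive its TAAE status from that date, and take its attributes only from that record and later ones.

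Where I10E-1302 and I10E-1306 adverse event records are not linked, require a new record dated at the worsening.

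Do not let a changed causality assessment alone trigger TEAE status. A late reassessment of an event that arose at the higher I10E-1302 dose is not a worsening at 0.5 g/kg.

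State whether the SOC/PT tables of SAEs and drug-related events are limited to TEAEs.

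The cost is some wording and one extra derivation. TEAE counts may rise slightly. Without linked records, sites also need an instruction on when to open a new entry.

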#### **3.1.4. Treatment Period**

Patients meeting all eligibility criteria will receive 1 dose of study drug at 0.5 g/kg over 1 to 2 day(s), every 3 weeks (+/- 7 days) for a total of 16 doses.

Investigators or Study Nurses will call patients 4 days (+/1 day) after the end of each study treatment course to document potential AEs and TAEs (see Section [8.2.2](#)).

Duration of the treatment period will be approximately 45 weeks.

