### **12.3. Sample Size Determination**

The number of patients included in this study depends on the number of responders in PRISM-I10E-1302 study willing to participate in the extension study. Estimated to be between 15 and 30 patients. Thus, no formal sample size calculation is done.

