### 2.3 SAMPLE SIZE

The number of patients included in this study depends on the number of responders in the I10E-1302 trial willing to participate in the extension study. Thus, no formal sample size calculation is done. The number of responders in the I10E-1302 trial is estimated to be between 15 and 30 patients.

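### Onset-time confidence intervals that pool courses count events, not patients, and will be too narrow if onset times correlate within patient

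*SAP*

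**What the plan says.** SAP 4.7.2 (Adverse Events) defines the time from the last administration of study drug to the onset of each TEAE and says that it "will be presented with descriptive statistics using the individual TEAE as statistical unit". Two paragraphs later it returns to the same variable for the commonest TEAEs, meaning "those which occurred in at least 10% of the patients". The display is split by whether the patient was naïve or pre-treated, and by course. The next sentence of the SAP reads: "Summary statistics including 95% confidence intervals will be calculated for each TEAE preferred term".

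The SAP does not say whether the interval is for a mean or a median, how it is calculated, or whether status and course number are crossed or shown separately. For this variable it has no first-event rule, no patient-level summary, no adjustment for repeated events and no minimum number of patients. The same section repeats the TEAE analyses for temporally associated events, so the intervals would appear there too.

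Protocol 3.1.4 schedules dosing "every 3 weeks (+/- 7 days) for a total of 16 doses". On numbers, Protocol 12.3 says "Estimated to be between 15 and 30 patients". SAP 2.3 applies that range to the parent study: "The number of responders in the I10E-1302 trial is estimated to be between 15 and 30 patients".

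**The concern.** An interval calculated over events treats its sample size as the number of events. If one patient has the same reaction after several courses, and at a similar delay each time, those events carry less information than the same number from different patients. The interval then shows mainly how consistent a few patients are with themselves, and says too little about differences between patients.

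The design leaves room for this. A patient can have up to 16 courses, and a term qualifies with very few patients. After a split into naïve and pre-treated, one stratum could rest on a single patient's repeated events. A reader of the report would take the printed 95% interval at face value and think onset timing better known than it is.

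**Working it through.** The plan states no width, variance, correlation or event count for these intervals, so there is no figure to reproduce. The check asks how an ordinary event-level interval behaves under stated assumptions.

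**Inputs from the documents.** Unit: single TEAE (SAP 4.7.2). Interval: 95% per common term (SAP 4.7.2). Planned courses: 16 (Protocol 3.1.4). Expected patients: 15–30 (Protocol 12.3).

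**Assumed, because the documents do not give them.** The within-patient correlation ρ of onset times, and the number of events per patient for a given term.

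**Step 1: patients needed to qualify.** 10% of 15 is 1.5, so 2 patients. 10% of 20 is 2. 10% of 21 is 2.1, so 3. 10% of 30 is 3. The minimum is therefore 2 patients for 15–20 treated and 3 for 21–30. This is a floor; commoner terms will have more.

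**Step 2: how much wider the interval should be.** With m events from each contributing patient, the variance of the mean is inflated by 1 + (m − 1)ρ, and the width by its square root:
- m = 1: factor 1.00 at any ρ.
- m = 2, ρ = 0.3: √(1 + 1 × 0.3) = √1.3 = 1.14.
- m = 4, ρ = 0.3: √(1 + 3 × 0.3) = √1.9 = 1.38.
- m = 8, ρ = 0.3: √(1 + 7 × 0.3) = √3.1 = 1.76.
- m = 16, ρ = 0.5: √(1 + 15 × 0.5) = √8.5 = 2.92, an upper case that uses every planned course.

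**Step 3: coverage.** The model is normal with a random patient effect, and a t-interval is calculated over all events. The results are simulated and good to about one percentage point. Each pattern lists the events contributed by each patient.

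| Pattern | ρ = 0.2 | ρ = 0.5 | ρ = 0.7 |
|---|---|---|---|
| 1,1,1 | 95% | 95% | 95% |
| 2,1,1 | 94% | 93% | 91% |
| 3,2,1,1 | 93% | 88% | 85% |
| 8,4,1 | 83% | 66% | 55% |
| 12,4,2,1 | 78% | 58% | 48% |
| 10,1 | 76% | 53% | 40% |

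At ρ = 0 coverage is 95% for every pattern. The 1,1,1 row is the usual situation inside a single-course cell, where a patient will normally have at most one event of a given term.

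**Step 4: the patient-level alternative.** A t-interval on one median per patient holds about 95–97% in the same simulations. Its cost is width. With 3 patients, 4 events each and ρ = 0.3, the mean width is 3.03 standard deviations, against 1.18 for the event-level interval, whose coverage there is 84%. With one value per patient, the mean width is about 14 standard deviations for 2 patients, 4.4 for 3, 2.3 for 5 and 1.4 for 10.

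**The case against.** The strongest reply has four parts.

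*The SAP never says that events are independent.* The unit is set in a sentence about descriptive statistics for all TEAEs, and the interval sentence names no method. A reader might infer that independence is declared, and it is not. This stands as a matter of wording. But the variable is the same and no other unit or method is offered, so an event-level interval is what a programmer following the text would produce.

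*Not all the intervals are affected.* Onset time is also shown by course number, and with one event per patient coverage stays at 95%. This stands, and it limits the point to intervals pooled over courses.

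*Heavy repetition may be unlikely.* Sixteen courses is a planned maximum. Relapsing patients are withdrawn (Protocol 3.1.6), and the study was stopped early because of relapses (SAP 4.10). No passage shows that the same patients have repeated infusion reactions. A reader might take coverage near 40% as the expected result, or 2–3 patients as the typical number behind a common term. The documents support neither: the first is an assumed extreme, the second the minimum to qualify.

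*Little depends on it.* SAP 3.4 calls the study purely descriptive, with no hypotheses tested, and SAP 4.7.2 already plans patient counts by system organ class and preferred term. This stands on importance. Those counts do not appear in the onset table or its strata, however, and an interval labelled 95% should still behave like one.

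**Conclusion.** The point holds for intervals pooled over courses, either overall per preferred term or by naïve/pre-treated status. It needs two conditions: positive correlation of onset times within patient, and more than one event of a term from at least one contributing patient. The documents establish neither.

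The size therefore ranges from nothing, at zero correlation or one event each, to serious. Under assumed correlations of 0.2–0.7, coverage is about 91–94% for mild repetition (2,1,1) and about 40–76% for heavy repetition (10,1). The conclusion that every onset-time interval in the section is invalid would go too far, because single-course cells are essentially sound. No endpoint, test or decision uses these intervals, so the impact is low. It is worth correcting because the stated unit leads to the wrong error bars and the correction is cheap.

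**What to change.** In SAP 4.7.2, for TEAEs and for the repeat in temporally associated events:

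- For any interval pooled over courses, use one value per patient and preferred term, for example the patient's median onset time. Calculate a t-interval across patients and label it as describing the typical patient, since this is a different quantity from the typical event.
- Keep the event-level summaries, but without a confidence interval.
- Print the number of contributing patients beside the number of events in every stratum.
- Omit the interval where only a few patients contribute, and set the minimum before database lock. The documents imply no particular cut-off; the widths in step 4 show what is at stake in choosing one.

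Resampling whole patients is not a good substitute here. A percentile bootstrap by patient covered only about 82% at correlations of both 0.2 and 0.5 for five patients with 12, 3, 2, 1 and 1 events.

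The cost is a few lines of programming and no new data. The drawback is that intervals for rare terms will be wider or absent.

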#### Temporally Associated Adverse Events (TAAEs)

The following rules for the derivation of the TAAE status will be used in the order of display.

1. If the exact date-time of the AE onset is known this information will be used: TAAE = "Yes" if AE onset date-time  $\geq$  start date-time of previous IMP infusion and (AE onset date-time – end date-time of previous IMP infusion)  $\leq$  72 hours / "No" otherwise".
2. If the exact date-time of onset is not known and the investigator's assessment of the time of onset is not missing: TAAE = "Yes" if investigator's assessment of AE onset time is either "During infusion" or " $\leq$ 72h" / "No" otherwise".
3. If the exact date-time of onset is not known, the investigator's assessment of the time of onset is missing and the exact date of onset of the AE is known: TAAE = "Yes" if AE onset date is on the same day than an IMP infusion or within 3 days after an infusion / "No" otherwise".
4. TAAE = "No" otherwise.

The same analyses as for TEAEs will be repeated for the TAAEs, i.e. AEs which started within 72 hours of an infusion. For the determination if an AE started within the 72 hours of an infusion the date-time of onset of the AE outweighs the investigator's answer to the question if the AE occurred *Before infusion / During infusion / Within 72 hours after end of infusion / More than 72 hours after end of infusion*. The investigator's answer to this question is only considered for the determination of TAAE if the date-time of AE onset is not precise enough to make a clear decision (i.e. time missing and date on the same date as an infusion or three days after the end of the previous infusion, incomplete date of onset).

The summary table on TAAEs will be presented twice:

- Using the patient as statistical unit
- Using the individual infusion as statistical unit

